## Study Assessments

Day	1	1	1	2	3	4	5
Time, hours	-1 to 0	0	0-T	NA	NA	NA	NA
Baseline assessments a	X						
Study drug administration		X e		X f	X f	X f	
Observation b			X			X c	X c
Patient reported events c				X	X	X	X
Concomitant medications d	X	X	X	X	X	X	X
Adverse events		X	X	X	X	X	X

### Notes:

aHistory, physical including VS (pulse, respiratory rate, blood pressure, temperature and, at baseline only height and weight), informed consent. For all patients: CBC with platelet count, biochemical profile and ECG. Urinalysis is required for all patients  $\geq$  age 40 and with a history of diabetes; it is optional for other patients. Blood and urine specimens should be taken expeditiously at the beginning of assessment, but patient entry into the study and treatment need not wait for lab results (other than pregnancy test and fingerstick blood glucose when required) unless clinically indicated. After phlebotomy, a saline lock may be placed so that the patient will not require an additional needle stick should he/she require intravenous fluids subsequently. History of present illness should include questioning regarding precipitating/causative factors, as well as recording of number and character of emetic and diarrheal episodes.

Patients with diet-controlled type 2 diabetes mellitus are to have a finger stick blood glucose.

For women of childbearing potential, as defined in the exclusion criteria: urine or serum pregnancy test. Negative pregnancy test result must be obtained prior to treating a patient on study.

bPatients are to be observed in the emergency department for a minimum of 4 hours after initial dose of study medication, with VS at least once every hour and recording of intake (both oral and parenteral) and number of voidings. All episodes of vomiting and diarrhea are to be recorded, and severity of nausea at baseline and every hour while in the ED noted.

All patients are to have a repeat ECG 4±0.25 hours after initial dosing with study medication. At a minimum of 4 hours after initial administration of study medication, after repeat ECG, patients may be discharged when clinically appropriate. **Any patient who has an on-study ECG showing QTc>500 msec must have a follow-up ECG showing resolution of the QTc prolongation. Timing of follow-up ECG(s) at investigator discretion. If the QTc does not decrease below 500 msec during follow-up, the medical monitor must be contacted to discuss further follow-up.**

cPrior to discharge, patients will be given diary pages to record their course after discharge. Patients will be contacted each day following treatment to a maximum of 4 days to determine whether they had further nausea and vomiting after leaving the emergency department, the occurrence and quality of bowel movements, including assessment using the Bristol stool scale (Appendix I), and the nature, occurrence and severity of other symptoms, whether they required further care for the acute gastroenteritis, and details regarding the continuation, if any, of the illness. If symptoms persist for 3 or more days after study entry, the patient is to be instructed to return for further evaluation.

dTo include all medications taken within 7 days prior to study entry, all treatments (including parenteral fluids) on the day of study entry, and all medication, including rescue medications, from the time of study entry through last follow-up.

ePatients are to receive the first dose of study medication within one hour of signing informed consent.

fPatients may take study medication daily for up to 3 days after study entry (maximum total of 4 doses, plus one additional if patient vomits within 15 minutes of first dose) if symptoms persist. Patients should stop taking study medication if symptoms have resolved, though they may resume study medication once daily if symptoms recur after discontinuation. Patients are not to take any remaining study medication after day 4. They will be given mailers to return any unused study medication.

## List of Abbreviations

°C	degrees Celsius
β-HCG	beta-human chorionic gonadotropin
5-HT3	5-hydroxytryptamine 3
AE	adverse event
ALT	alanine aminotransferase
AST	aspartate aminotransferase
BUN	blood urea nitrogen
CBC	complete blood count
CFR	Code of Federal Regulations
CO 2	bicarbonate
CRF	case report form
ED	Emergency department (emergency room)
FDA	Food and Drug Administration
GCP	Good Clinical Practices
HIPAA	Health Information Portability and Accountability Act
ICH	International Committee on Harmonisation
IRB	institutional review board
Kg	Kilogram
MedDRA	Medical dictionary for regulatory activities
Mg	Milligram
NCI-CTCAE v 4	National Cancer Institute common terminology criteria for adverse events, version 4
SAE	serious adverse event
VS	vital signs
vs	versus
WBC	white blood count
WOCBP	women of childbearing potential

## **1. Background and Rationale**

### **1.1 Acute Gastroenteritis**

Acute gastroenteritis is inflammation of the stomach, small intestine or large intestine, leading to a combination of abdominal pain, cramping, nausea, vomiting and diarrhea (Graves, 2013). Acute gastritis is inflammation of the stomach; patients with acute gastritis may have vomiting without diarrhea. For purposes of this protocol, patients must present with at least vomiting, as described below, with or without other symptoms.

Acute gastroenteritis is a major health problem worldwide. While mortality is greatest in developing countries and in both the very young and old, morbidity of acute gastroenteritis is shared by all ages and economic strata. In the US, most cases of acute gastroenteritis are viral, most commonly rotavirus and norovirus (Chow et al, 2010; Graves, 2013). In the US, there are between 15-25 million episodes of viral gastroenteritis annually, leading to 3-5 million office visits and 200,000 hospitalizations. While mortality is low, among the 17,000 people dying from acute gastroenteritis in the US each year, 83% are over age 65 (CDC, 2012).

Most cases are self-limited, resolving in one to several days. Mild to moderate cases are generally treated symptomatically. In children, there are guidelines for oral rehydration therapy. More severe and prolonged cases may require diagnostic studies for etiologic organisms. Depending on the severity and etiology, treatment varies from dietary modifications, including oral rehydration therapy, to intravenous fluids and antibiotics. Antiemetics and antidiarrheals are often used. Prochlorperazine and perphenazine are both approved for treatment of nausea and vomiting in general, i.e., including for treatment of acute gastroenteritis. Several other products approved for treatment of nausea and vomiting in special situations, e.g., postoperatively or in association with cancer chemotherapy, are also used for this indication. Ondansetron is often used in both children and adults with acute gastroenteritis, but has never been approved for this indication in any country.

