Endpoints Efficacy:	
Primary:
 
Absence of vomiting without use of rescue medication or parenteral hydration from 30 minutes through 24 hours after the first dose of study medication.
 
Secondary:
 

• Treatment success, as defined above, through 4 days following first dose of study medication

• Individual components of treatment failure through 4 days following first dose of study medication:

◦ Vomiting

◦ Requirement for rescue antiemetic

◦ Treatment with intravenous hydration

• Severity of nausea

• Diarrhea will be reported in two ways:

◦ Bristol Stool Scale (BSS): number and distribution by grade of grade <math>\geq 5</math> stools daily throughout the study

◦ Stool consistency, as recorded per prior versions of protocol, none/formed (normal)/soft/watery (diarrhea)

• Incidence and severity of other symptoms of gastroenteritis, as recorded in CRF and patient diaries

• Time from first dose of study medication to discharge from ED, extended observation unit or hospital, whichever comes last

	
 
• Time to resumption of normal activities (work/school/household)
 
• Hospital admission
 
• Return to emergency department for gastrointestinal symptoms
 
• 
 

Safety:	Incidence and severity of adverse events through time of last follow-up call

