#### 4.4 Concomitant Therapy

If deemed necessary by the investigator, patients may take rescue antiemetics, either orally or intravenously, as described in section 4.2, above. Also, if deemed necessary by the investigator, patients may receive parenteral hydration. However, every effort should be made to avoid both rescue medications and parenteral hydration, and to proceed with oral hydration, unless it is clear that the patient will not be able to tolerate oral hydration.

**From the time a patient takes any antiemetic other than study medication, whether while in or after leaving the emergency department, or receives parenteral hydration, he or she will be deemed a treatment failure, even in the absence of vomiting.**

Patients may take antipyretic and antidiarrheal medication as needed prior to or after initial dosing with study medication. Patients may also take medications for gastrointestinal symptoms as long as they are not specifically antiemetics. For

example, they may use proton pump inhibitors or antacids. Once vomiting is controlled, patients should resume any medications they routinely take.

Patients for whom an intravenous medication (other than antiemetic) is indicated once on study may receive that medication in up to 100 mL fluid. This will not be considered parenteral *hydration*. For example, if a patient has a urinalysis suggesting infection and the investigator or other physician wish to give the patient an intravenous antibiotic dose, that will not be considered treatment failure as long as the drug is given in ≤100 mL fluid.

If once on study, a patient requires a medication which may prolong the QTc interval, he or she should not receive further study medication. However, evaluation of the patient should continue per protocol.

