6. ANALYSIS SETS

6.1. Full Analysis Set

The intent-to-treat population (ITT) will consist of all patients who receive any study medication, even if they vomit shortly after administration or are unable to swallow the medication. The primary efficacy analysis will be conducted using ITT population.

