7. ENDPOINTS AND COVARIATES

7.1. Efficacy Endpoint(s)

- 1) Primary Efficacy Endpoint: the proportion of patients who fulfill all the following 3 criteria from 30 minutes after first administration of study medication until 24 hours after the first dose of study medication:
 - a. absence of vomiting
 - b. no use of rescue medication, and
 - c. no intravenous hydration

If all of the above three criteria are fulfilled, the patient is considered a treatment success for the primary analysis. If one or more of the above three criteria are not fulfilled, i.e., the patient either experiences vomiting, receives rescue medication or receives intravenous hydration from 30 minutes through 24 hours after the first dose of study medication, the patient is considered a treatment failure.

Based on the 2nd blinded dry run conducted on [REDACTED], there were 28 subjects who did not have all the information needed to determine per the algorithm used if they met the primary endpoint successfully. For 17 patients, all treated under amendment 1 or 2, in which the primary endpoint was treatment success on emergency department discharge, the reason for not having complete information was the lack of an ER day diary. For these patients, based on all follow up data available, no treatment failure events occurred. Therefore, these patients are considered treatment successes. Among the other eleven, data were reviewed and several queries issued. Based on this review, patients were assessed by the medical monitor to be treatment successes (n=4), failures (n=1) or unknown (n=6). The adjudicated primary endpoint outcomes will be used for the primary analyses.

2) Secondary and Tertiary Efficacy Endpoints:

- Treatment success, as defined above, through 4 days following first dose of study medication
- Proportion of patients who experience or require each of the components of treatment failure:
 - Vomiting
 - Rescue antiemetic therapy
 - Intravenous hydration
- Severity of nausea
- Incidence and severity of diarrhea
- Incidence and severity of other symptoms of gastroenteritis
- Time from first dose of study medication to discharge from ED, extended observation unit or hospital, whichever comes last
- Days to resumption of normal activities (work/school/household)
- Proportion of patients requiring hospitalization
- Proportion of patients returning to emergency department for gastrointestinal symptoms within 4 days of initial discharge

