9.3. Efficacy Analyses for Secondary and Tertiary Endpoints

ITT population will be used for the analyses of all secondary and tertiary endpoints.

1) Analyses of Binary/Proportion Endpoint

Same statistical test as for the analyses of the primary endpoint, as stated in Section 9.2, will be used for analyzing other proportion endpoints.

2) Analyses of Time-to-Event Endpoints

Time to event endpoints will be compared between the treatment arms using stratified log-rank test adjusting the age stratification factor. The endpoints will also be summarized using the Kaplan-Meier method and displayed graphically when appropriate. Median event times and 2-sided 95% confidence interval for each median will be provided.

3) Analyses of Continuous Endpoints

Descriptive statistics, including the mean, standard deviation, median, minimum, and maximum values, will be provided for continuous endpoints.

4) Analyses of Ordinal Categorical Endpoints

The number and percentage of patients in each category will be provided for categorical endpoints. Bristol Stool Scale (BSS), added in the Protocol Amendment 3, is an 8 point ordinal categorical variable. Wilcoxon rank sum test will be used to compare the two treatment groups.

5) Concordance Assessment of Bristol Stool Scale and Stool consistency

Stool consistency, as recorded per original protocol, none/formed (normal)/soft/watery (diarrhea), is a 4 point ordinal categorical variable. Cross-tabulation of stool consistency and BSS among all the patients who have both assessments at a given time point will be created to evaluate the concordance of the two scales. Cohen's Weighted Kappa Coefficient and 95% confidence interval will be provided.

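### Diarrhea comparisons ignore whether the patient had diarrhea at entry, so they mix persistence with new onset and are less efficient than the recorded baseline history allows

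*Protocol*

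**What the plan says.** - **Entry.** Protocol section 1.1 requires only vomiting ("patients must present with at least vomiting, as described below, with or without other symptoms") and notes that "patients with acute gastritis may have vomiting without diarrhea".
- **Baseline data.** Note a to the Study Assessments table asks for "recording of number and character of emetic and diarrheal episodes" in the history of present illness. It sets no look-back period.
- **Endpoint.** SAP section 7.1 lists "Incidence and severity of diarrhea" among the secondary and tertiary endpoints. The Protocol Synopsis has it measured by the Bristol Stool Scale and by the four-level consistency item of the original protocol.
- **Analysis set.** SAP section 9.3: "ITT population will be used for the analyses of all secondary and tertiary endpoints". SAP section 6.1: "The intent-to-treat population (ITT) will consist of all patients who receive any study medication".
- **Tests.** SAP section 9.3 gives the Bristol scale a two-group Wilcoxon rank sum test with no stratum. Proportions follow the primary analysis, a CMH test stratified by age.
- **Covariates.** SAP section 7.3 requires age as a covariate for primary and secondary endpoints, and the baseline value for continuous endpoints only. For continuous endpoints, section 9.3 then plans descriptive statistics alone.
- **Antidiarrheals.** Protocol section 4.4: "Patients may take antipyretic and antidiarrheal medication as needed prior to or after initial dosing with study medication". Neither document says how later stools are scored.

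**The concern.** Two kinds of patient enter the same comparison. In a patient with diarrhea at entry, a loose stool on day 2 shows that the illness persists. In a patient without it, the same stool is a new event. No diarrhea analysis in the SAP separates the two.

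This has two consequences. A difference between arms cannot be read as shortening diarrhea or as preventing it. And the large difference in stool burden between the two kinds of patient goes into the test as unexplained variation, although the variable that explains it is collected before dosing.

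The question matters to this trial: Protocol section 1.4 counts the constipating effect of ondansetron as a benefit in the intended indication, and diarrhea is a stated secondary objective.

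**Working it through.** **1. The plan's own figure.** The only sample size belongs to the primary endpoint. With 40% v 20% failure, two-sided 0.01, 90% power and 60:40 allocation, the pooled-variance formula gives 127 + 191 = 318, against 320 stated. Power at 128/192 is 90.4%. No power, stool rate or share with diarrhea at entry is given for the diarrhea endpoint. Every diarrhea input below is therefore an assumption, tested at two-sided 0.05.

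**2. Mixing, by arithmetic.** Let f be the share with diarrhea at entry. The all-treated difference is f × (difference in persistence) + (1 − f) × (difference in new onset).
- f = 0.6, persistence 60% v 42%, new onset 20% in both arms: 0.6 × 18 + 0.4 × 0 = 10.8 points.
- f = 0.4, the same persistence, new onset 20% v 14%: 0.4 × 18 + 0.6 × 6 = 10.8 points.

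The first drug does not prevent diarrhea and the second does, yet the planned analysis shows the same difference for both.

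**3. Power for the Wilcoxon test, stool counts.** Model: 192/128 patients, daily loose stools negative binomial with dispersion 1, rate ratio 0.65 in both entry groups. The comparator is a van Elteren test with strata by entry diarrhea and weights 1/(n + 1). I ran 6,000 trials per setting, so the Monte Carlo standard error is at most about 0.6 points.

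| Share with entry diarrhea | Mean stools with / without | Wilcoxon | van Elteren | Gain |
|---|---|---|---|---|
| 50% | 4.0 / 0.4 | 42% | 64% | 22 |
| 60% | 4.0 / 0.4 | 48% | 69% | 21 |
| 70% | 4.0 / 0.4 | 55% | 71% | 17 |
| 90% | 4.0 / 0.4 | 72% | 78% | 6 |
| 60% | 4.0 / 1.0 | 63% | 74% | 11 |
| 60% | 4.0 / 2.0 | 75% | 77% | 3 |

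Gains are taken before rounding. With rate ratio 1, both tests reject in about 5% of trials. If the drug acts only in patients with entry diarrhea, the gain in these settings is 1 to 14 points.

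**4. The same test on an ordinal scale.** SAP section 9.3 assigns the Wilcoxon test to scale grades, so I repeated the check on an assumed four-level scale (none, formed, soft, watery). With entry diarrhea: placebo 10/15/25/50%, active 18/22/25/35%. Without: placebo 45/40/10/5%, active either the same or 52/40/5.5/2.5%. For f from 0.4 to 0.8 the gain is about 3 to 12 points. At f = 0.6 it is 40% v 46% with no effect on new onset, and 60% v 72% with one.

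**5. Incidence by CMH.** Take f = 0.6, persistence 60% v 42%, new onset 20% v 14%. The all-treated rates are 0.6 × 60 + 0.4 × 20 = 44% and 0.6 × 42 + 0.4 × 14 = 30.8%, a difference of 13.2 points.
- Unstratified: null SE 0.0548, alternative SE 0.0551; z = (0.132 − 1.96 × 0.0548)/0.0551 = 0.45, power 67%.
- Stratified, same difference: null SE 0.0516, alternative SE 0.0514; z = (0.132 − 1.96 × 0.0516)/0.0514 = 0.60, power 73%.

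With no effect on new onset the figures are 50% v 53%. With 80% v 60% persistence and 20% v 15% new onset they are 69% v 82%.

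**6. Actual data are fewer.** Protocol section 5.2.3 gives patients who fail within 24 hours a single call after the ED. At the plan's failure rates that is 0.40 × 128 + 0.20 × 192 = 51.2 + 38.4 = 89.6 patients, 28% of 320. The Bristol scale began only with Amendment 3. The absolute powers above are therefore not the trial's; the contrast between the tests is the point.

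**The case against.** **It is not bias.** A reader might infer that the planned comparison is invalid. It is not: entry diarrhea is a pre-randomization variable, and both tests hold their level. An all-treated comparison of stool burden also answers the objective as written, which does not ask for persistence and new onset separately. This stands. Missing post-ED stool data are a different limitation.

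**The power loss is conditional.** The size comes from assumed stool means and shares, and the documents supply neither. That stands, which is why a range is given. Nor does the point support restricting the analysis to patients with entry diarrhea. With 60% v 42% persistence and 20% v 14% new onset, that subset gains little at f = 0.6 (69% v 67% for all treated) and loses at f = 0.4 (51% v 55%). Stratification keeps everyone, and gives 73% and 60% in those two cases.

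**The SAP already adjusts for baseline.** SAP section 7.3 does so for continuous endpoints only. The Bristol scale is classed as ordinal, and section 9.3 gives no model for continuous ones.

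**Antidiarrheals.** A reader might infer that free antidiarrheal use masks the effect and should count as failure, as a rescue antiemetic does. The documents do not support this. Antidiarrheals are permitted background therapy, not a component of any defined failure, and scoring stools as observed is inferred from silence. The dilution is also only as large as the assumed use. For true rates of 45% v 60% and a drug that works in half of users, 40% use turns them into 36% v 48% and power falls from 75% to 57%. At 10% use it falls only to 71%. Counting every day from first use as a loose-stool day would also misclassify patients who took a dose before study entry and had no later loose stool. Only a descriptive table is warranted.

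**Conclusion.** The point holds as one of efficiency and interpretability. The diarrhea comparisons pool patients with and without diarrhea at entry although the distinguishing history is collected, and the Wilcoxon test leaves out even the age factor that SAP section 7.3 prescribes.

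Stratifying gained power in every non-null setting tried: about 3 to 22 points for stool counts with a common drug effect, less if the drug acts only on existing diarrhea, and 3 to 13 points in the CMH examples. All of this assumes 192/128 with complete data and entry shares and stool rates that the documents do not give.

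Diarrhea is a secondary endpoint with no stated power. Nothing here touches the primary conclusion.

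**What to change.** In SAP section 9.3:

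1. Define diarrhea at entry (yes/no) from the note a history, with a stated look-back period.
2. Stratify the diarrhea comparisons by entry diarrhea and age: a van Elteren test for the stool scale, CMH over both factors for incidence. State in advance how sparse cells are collapsed, since the group under 18 may be small. This also brings the stool-scale test into line with SAP section 7.3.
3. Show results separately for patients with diarrhea at entry (persistence) and without (new onset).
4. Tabulate antidiarrheal use by arm from the concomitant medication record, before and after dosing, as description only.

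The cost is SAP wording and two short tables; no new data are needed. The Supplemental SAP records unblinding on June 3, 2017, so any such analysis added now must be labeled supportive. That document already adds covariate-adjusted analyses after unblinding, so there is a place for it.

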### **1.2 Ondansetron for Acute Gastroenteritis**

Ondansetron has been studied in several studies in acute gastroenteritis, primarily in children (Chow et al, 2010). In seven studies, either intravenous (3 studies) or oral (4 studies) ondansetron was compared against placebo, and in two intravenous ondansetron was compared against active agents. Most of the studies against active agents demonstrated a significant decrease in the proportion of patients with vomiting subsequent to dosing. Overall, the proportion of patients with vomiting in the emergency department after ondansetron was about half that after placebo. Only one study, comparing ondansetron with prochlorperazine, was entirely in adults, and one additional study, with ondansetron compared to placebo, was in children and adults, though most participants were children. Thus, ondansetron has not been studied extensively in clinical trials in adults with acute gastroenteritis.

